T1DM type 1 diabetes
t-PA tissue plasminogen activator
U&E urea and electrolytes
ULN upper limit of normal
UKPDS United Kingdom Prospective Diabetes Study

1. STUDY SYNOPSIS

Title of Study:	REducing with MetfOrmin Vascular Adverse Lesions in T1DM (REMOVAL)
Brief Title:	REMOVAL
National Coordinating Centres	British Heart Foundation: Glasgow Cardiovascular Research Centre, Glasgow; Steno Diabetes Center, Gentofte; University of Western Ontario, London, Ontario; NHMRC Clinical Trials Centre, Sydney Medical School, Australia; University of Maastricht, Netherlands
Duration of Study:	Three month run-in period (third month with single-blind placebo); 3 years double-blind randomized treatment.
Primary Objective:	To assess in a randomized controlled trial the effects of three years metformin added to titrated insulin therapy (towards target HbA1c 7.0%/ 53 mmol/mol) on progression of atheroma as measured by progression of averaged mean far wall common carotid artery intima-media thickness (cIMT) in adults with type 1 diabetes at risk of cardiovascular disease.
Secondary Objectives:	Change in: (i) HbA1c; (ii) LDL cholesterol; (iii) albuminuria and estimated glomerular filtration rate; (iv) retinopathy stage (two-field photographs); (v) weight; (vi) insulin dose; (vii) endothelial function
Tertiary Objectives:	Change in: (i) frequency of hypoglycaemia; (ii) treatment satisfaction; (iii) markers of endothelial function (t-PA, sE-selectin, sICAM-1); (iv) progression of mean maximal distal common carotid artery cIMT; (v) vitamin B12 status.
Rationale:	
Intensive glucose control reduces long term rates of cardiovascular disease (CVD) in people type 1 diabetes (T1DM) but the majority of individuals affected by the condition do not currently achieve glucose targets with standard insulin therapy. Upward insulin dose titration may lead to weight gain, hypoglycaemia and dyslipidaemia. Metformin has potential for addressing these issues as it may: (i) reduce insulin dose for a given achieved HbA1c; (ii) promote weight stabilization; (iii) be associated with low rates of hypoglycaemia; and (iv) reduce LDL cholesterol - even on a background of statin therapy. It may also have direct and potentially beneficial cardiovascular effects.
 
Progression of carotid artery intima-media thickness (cIMT) is the primary endpoint as this is accelerated in type 1 diabetes. cIMT reliably predicted cardiovascular events in DCCT and has been successfully targeted by metformin in a number of small studies in conditions other than type 1 diabetes. The secondary endpoint is a composite of clinically-relevant markers of microvascular and macrovascular prognosis.

Product, Dose, Modes of Administration:	
Single-blind placebo Run-In: One tablet once daily with the evening meal.
 
Double-blind treatment period: Oral metformin (as Glucophage 500 mg x 2 twice daily) titrated from initial 500 mg to target 2000 mg daily/ matching placebo.

Sample Size:	500 enrolled participants.
Randomisation:	By telephone call to the study Interactive Voice Response System (IVRS) or electronically via the portal providing the study electronic Case Report Form (as provided by the Robertson Centre for Biostatistics, University of Glasgow).

Inclusion Criteria (abbreviated)	
Type 1 diabetes (defined in Section 7.1) for five years or more; age ≥ 40 years; $7.0 \leq \text{HbA1c} < 10.0\%$ (53-86 mmol/mol)
 
AND three or more of the following ten CVD risk factors:
 
 (i) BMI $\geq 27 \text{ kg/m}^2$ (ii) current HbA1c $> 8.0\%$ (64 mmol/mol) (iii) known CVD/ peripheral vascular disease (iv) current smoker (v) eGFR $< 90 \text{ ml/ min/ } 1.73 \text{ m}^2$ (vi) confirmed micro- (or macro-) albuminuria [according to local assays and reference ranges] (vii) hypertension (BP $\geq 140/ 90 \text{ mmHg}$; or established on antihypertensive treatment) (viii) dyslipidaemia [total cholesterol $\geq 5.0 \text{ mmol/L}$ (200 mg/dL); or HDL cholesterol $< 1.20 \text{ mmol/L}$ (46 mg/dL) [men] HDL cholesterol $< 1.30 \text{ mmol/L}$ (50 mg/dL) [women]; or fasting triglycerides $\geq 1.7 \text{ mmol/L}$ (150 mg/dL); or established on lipid-lowering treatment (ix) strong family history of CVD (at least one parent, biological aunt/ uncle, or sibling with myocardial infarction or stroke aged < 60 years) (x) duration of diabetes > 20 years.
Exclusion Criteria (abbreviated)	
 (i) eGFR $< 45 \text{ ml/ min/ } 1.73\text{m}^2$ (ii) woman of childbearing age not on effective contraception – see Appendix 4 (iii) pregnancy and/or lactation (iv) Acute Coronary Syndrome or Stroke/ TIA within the last 3 months (v) NYHA stage 3 or 4 heart failure (vi) uncontrolled angina (vi) significant hypoglycaemia unawareness (vii) impaired cognitive function/ unable to give informed consent (viii) previous carotid surgery/ inability to capture adequate carotid images (ix) gastroparesis (x) history of lactic acidosis (xi) other contraindications to metformin 
 - hepatic impairment - known hypersensitivity to metformin - acute illness (dehydration, severe infection, shock, acute cardiac failure) - suspected tissue hypoxia (xii) Any coexistent life threatening condition including prior diagnosis of cancer within two years (xii) history of alcohol problem or drug abuse
Duration of Treatment:	Three years per participant (plus one month placebo single-blind in third month of three month Run-In period)
Statistical Analysis Primary:	Mixed effects regression model estimates of between-group cIMT differences over time, with 95% confidence intervals and p-values. Primary outcome regression model extended to assess whether metabolic effects could explain differences in progression of cIMT.

2. SCHEDULE OF ASSESSMENTS

Protocol: REMOVAL																							
	Pre-screening	Run-in Period				Treatment																	
telephone visit only R routine clinic visit F fasting visit	Visit 0 ^R	Visit R1	Visit R2	Visit R3*	Visit R4*	Visit 1 ^F	Visit 2*	Visit 3*	Visit 4*	Visit 5 ^R	Visit 6 ^R	Visit 7*	Visit 8 ^F Yr 1	Visit 9*	Visit 10 ^R	Visit 11*	Visit 12 ^F Yr 2	Visit 13*	Visit 14 ^{R 1}	Visit 15* ¹	Visit 16 ^F Yr 3	Visit 17 ² Close out	
Treatment month (± 2 weeks; or see Appendix 6)		-3		-2	-1	0			1	3	6	9	12	15	18	21	24	27	30	33	36	38	
Treatment week (± 3 days)			-10	-8	-4		1	2															
Provide information	x																					x	
Informed consent		x																					
Eligibility criteria		x																					
Medical/ Disease History		x																					
Concomitant medications		x				x			x	x	x	x	x		x		x		x		x		
Weight ^R		x				x				x	x		x		x		x		x		x		
Waist circumference		x				x				x	x		x		x		x		x		x		
Height ^R		x																					
BP and heart rate ^R		x				x					x		x		x		x		x		x		
Dispense study medication		x				x				x	x		x		x		x		x		x		
Collect/ count unused medication						x				x	x		x		x		x		x		x		
Titrate study medication							x	x	x														
Give out new diary		x				x					x				x					x			
Adjust insulin to HbA1c (review glucose diary) ^R		x	x	x	x	x	x	x	x	x	x	x	x	x	x	x	x	x	x	x	x	x	
Record insulin dose						x	x	x	x	x	x	x	x	x	x	x	x	x	x	x	x	x	
Steno hypoglycaemia questionnaire		x				x			x	x	x	x	x	x	x	x	x	x	x	x	x	x	
Treatment satisfaction questionnaire		x				x							x				x					x	
Other adverse events (including cardiovascular)			x	x	x	x	x	x	x	x	x	x	x	x	x	x	x	x	x	x	x	x	
Full blood count, vitamin B12 ^R		x				x							x				x					x	
U+E, local lab HbA1c, LFT, routine lipids ^R		x				x				x	x		x		x		x		x		x		
Pregnancy test		x				x	Only in women of childbearing age – repeated if clinically indicated in prompted discussion with participant																
C-peptide		x																					
Carotid IMT (± 4 weeks except Visit 1: see below**)						x							x									x	
Retinal images (± 4 weeks except Visit 1: see below**)						x																x	
Endothelial function (ENDOPAT) (± 4 weeks except Visit 1: see below**)						x							x									x	
LDL sample for central analysis		x				x							x				x					x	
Microalbuminuria ^R		x				(x)							x				x					x	
Lactate						x				x			x				x					x	
Plasma biomarker samples		x				x							x				x					x	
Urine aliquot		x				x							x				x					x	

** N.B. All Visit 1 assessments [including carotid IMT, retinal imaging and ENDOPAT] MUST be completed within 4 weeks PRIOR TO randomization**

¹ VISIT 14 and VISIT 15 time windows altered or omitted for participants randomized after the end of March 2014 – see Appendix 6 ² VISIT 17 must be at least one week after Visit 16

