In these cases, treatment will be restarted where possible in accordance with the Investigator's clinical judgement, local practice, standard-of-care, and national guidelines (renewed titration from a lower starting dose is not usually required unless interruption has been prolonged e.g. more than four weeks). Where treatment interruption has persisted for four weeks or more it will be documented as permanent.

Withdrawal of treatment: Investigators will withdraw from treatment any participant who develops any of the following:

- Pregnancy: discontinue if participant becomes, or intends to become, pregnant
- Development of new contraindications to metformin
 - o hepatic impairment (ALT > 3.0 ULN)
 - o renal impairment with eGFR <30 mL/min/1.73m² during study – see page 28
- Biochemically-confirmed severe lactic acidosis (>5.0 mmol/L with acidosis)
- Hypersensitivity to metformin

Dose reduction of treatment: Where eGFR falls below 45 ml/min/ 1.73m² on any measurement Investigators should permanently reduce metformin dose to 500 mg twice daily.

Withdrawal from study: Investigators will withdraw from the study any randomized participants with:

[figure not shown]
- confirmed pregnancy
- withdrawal of consent for follow-up
- any other reason agreed between the participant and the site Principal Investigator

At the end of the study: No further study medication will be provided.

Assessment of adherence: Tablet counts will be carried out by study nurses following at relevant study visits, including the final clinic visit, to assess adherence. This will be documented in the eCRF. Site medical and nursing staff will also discuss and reinforce adherence to study medication with participants.

Concomitant medication. No concomitant medication is specifically excluded.

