Study Visit 12 (24 months). Vital signs, weight, waist circumference. Carotid IMT. Dispense study medication. Collect unused medication. Hypoglycaemia questionnaire. Treatment satisfaction questionnaire. Insulin dose titration/ record insulin dose. Blood samples (U&E, LFT, HbA1C, local laboratory total cholesterol, HDL and triglycerides, FBC, vitamin B12, lactate), microalbuminuria status. Samples for LDL, plasma

biomarkers. Urine aliquot. Pregnancy testing if appropriate. Concomitant medications recorded. Questions on adverse events.

Telephone Visit 13 (27 months). Insulin dose titration/ record insulin dose. Hypoglycaemia questionnaire. Questions on adverse events.

Study Visit 14 (30 months – omitted for participants randomized after September 2014 as per Appendix 6). Vital signs, weight, waist circumference; U&E, LFTs, HbA1c as per routine care. Insulin dose titration/ record insulin dose. Give out diary. Hypoglycaemia questionnaire. Dispense study medication. Collect unused medication. Any change in concomitant medications will be recorded. Questions on adverse events.

Telephone Visit 15 (33 months – omitted for participants randomized after June 2014 as per Appendix 6). Insulin dose titration/ record insulin dose. Hypoglycaemia questionnaire. Questions on adverse events.

Study Visit 16 (36 months - earlier for participants randomized after March 2014 as per Appendix 6). Vital signs, weight, waist circumference. Carotid IMT. Retinal imaging. Endothelial function. Hypoglycaemia questionnaire. Treatment satisfaction questionnaire. Insulin dose titration/ record insulin dose. Blood samples (U&E, LFT, HbA1C, local laboratory total cholesterol, HDL and triglycerides, FBC, vitamin B12, lactate), microalbuminuria status. Samples for LDL, plasma biomarkers. Urine aliquot. Pregnancy testing if appropriate. Collect all unused medication. Concomitant medications recorded. Questions on adverse events.

Close out Visit 17 (at least one week after Visit 16 but within two weeks). Insulin dose titration following withdrawal of randomized medication. Provide information. Remaining study medication will be sent to pharmacy for tablet count. Questions on adverse events.

Unscheduled visit (at any time): Adverse event reporting; treatment dose reduction or discontinuation; lost medication.

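### The Visit 16 ENDOPAT window runs up to 4 weeks past the collection of study drug, so an in-window test can be off treatment and is analysed as an ordinary month-36 value

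*Protocol*

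**What the plan says.** **Test windows.** Section 2 of the protocol gives the final vascular tests a two-sided allowance: "Endothelial function (ENDOPAT) (± 4 weeks except Visit 1: see below", and likewise "Carotid IMT (± 4 weeks except Visit 1: see below". Retinal images carry the same allowance. The only one-sided rule is for Visit 1, whose assessments "MUST be completed within 4 weeks PRIOR TO randomization". The clinic visits themselves have a narrower window: "Treatment month (± 2 weeks; or see Appendix 6".

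**Drug at the end of the trial.** Section 10 lists carotid IMT, retinal imaging and endothelial function at Visit 16, with the instruction "Collect all unused medication" and no dispensing. Visit 17 is described as "Close out Visit 17 (at least one week after Visit 16 but within two weeks", and its first task is "Insulin dose titration following withdrawal of randomized medication". Under the end of the study, Section 8 states "No further study medication will be provided".

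**Measurement and analysis.** Section 6(b) schedules ENDOPAT at 0, 12 and 36 months in about 400 of the 500 participants. SAP 2.4.2 models change from baseline with visit as a class variable and takes the treatment main effect as the main test. SAP 1.6.2 and 2.1 use all available data whatever the adherence. Endothelial function is one of the secondary outcomes counted in the rule that significant improvement in at least two of them is clinically meaningful (protocol Section 5, SAP 2.4.2).

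**The concern.** The ENDOPAT window extends beyond the visit at which drug is taken back, and nothing requires the final test to come first. At Visit 8 a late test does no harm, because treatment continues. At Visit 16 a late test falls after treatment has ended by design.

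Reactive hyperaemia is a functional measure, so a treatment effect on it may not persist once tablets stop. The objective is the effect of three years of treatment, and a test after the regimen has ended need not measure that. Because visit enters the model as a class variable, a test 4 weeks off drug is indistinguishable from one on drug. The Per Protocol analysis covers only the primary outcome, so it would not remove such tests either. Any resulting error is toward no effect, in an outcome with only two post-baseline measurements.

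**Working it through.** **Step 1. Can an in-window test be off drug?**
- Window counted from the actual Visit 16: up to 4 weeks after drug collection.
- Both windows counted from nominal month 36, with the test on the last permitted day: 4 − 2 = 2 weeks after a Visit 16 held two weeks late, or 4 + 2 = 6 weeks after one held two weeks early.

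The window passes drug collection on either reading.

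**Step 2. The plan's own power figures.** Use the two-sample normal formula, power = Φ(δ√(n/2) − 1.96), with δ in SD units and n per arm.
- Primary (protocol 6(d)): 0.0167 mm, SD 0.05 mm, 200 per arm gives 91.6%, against the stated 90%. The minimum is 189 per arm, so the plan's figure reproduces with rounding up.
- Other continuous outcomes (protocol 6(d), about 0.3 SD at 90%): 0.3 SD gives 85.1% at 200 per arm and 91.8% at 250 per arm. At 200 per arm, 90% power needs 0.324 SD, which fits the protocol's approximate wording.

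**Step 3. ENDOPAT sample.** About 400 tested is 200 per arm. Less 20% drop-out (the lower end of the protocol's 20–25%), this is 160 per arm. Undiluted power for 0.3 SD: 0.3 × √80 = 2.683, and Φ(2.683 − 1.96) = 76.5%.

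**Step 4. Dilution.** Let f be the share of Visit 16 tests done after drug collection and r the share of the effect that remains. Both are assumptions; the documents give neither. Month 12 is undiluted, and the two visits are weighted equally.
- Visit 16 effect multiplier: 1 − f(1 − r)
- Pooled effect multiplier: 1 − f(1 − r)/2

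| f | r | Visit 16 effect left | Pooled effect left | Power, 160 per arm | Power, 200 per arm |
|---|---|---|---|---|---|
| 0 | – | 100% | 100% | 76.5% | 85.1% |
| 10% | 0 | 90% | 95% | 72.2% | 81.3% |
| 25% | 0 | 75% | 87.5% | 65.1% | 74.7% |
| 50% | 0 | 50% | 75% | 52.1% | 61.4% |
| 10% | 0.5 | 95% | 97.5% | 74.4% | 83.3% |
| 25% | 0.5 | 87.5% | 93.75% | 71.1% | 80.3% |
| 50% | 0.5 | 75% | 87.5% | 65.1% | 74.7% |

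Example, f = 25% and r = 0 at 160 per arm: 2.683 × 0.875 = 2.348, and Φ(0.388) = 65.1%.

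**Step 5. The carotid endpoint.** Suppose the cIMT slope returns to the control slope when drug stops. A scan m months off drug then loses 1 − 36/(36 + m) of the difference expected had treatment continued to the scan. For 2, 4 and 6 weeks (m = 0.46, 0.92, 1.38) this is 1.3%, 2.5% and 3.7%. That is negligible for the primary analysis.

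**The case against.** **The expected case is on drug.** ENDOPAT is listed as a Visit 16 procedure, and the extra 4 weeks is an allowance for late bookings. Nothing suggests that sites used it often. This stands: the text shows what is permitted, not what is common.

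**The documents are not uniform about the end of treatment.** As extracted, the schedule carries a dispensing mark at Visit 16, against Section 10; this may be a table-reading fault. Section 13 has remaining medication collected at the last visit, and Visit 17 sends remaining medication to pharmacy for a count. These conflicts need settling, but the Visit 17 wording and Section 8 both point to no drug after Visit 16.

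**The three-week rule.** Section 15 counts visit attendance more than three weeks from the intended date as a deviation, so it is arguable whether a test in week 4 is compliant. A test up to three weeks late is unaffected by that argument, and the rule removes no ENDOPAT value from the analysis.

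**All data are analysed whatever the adherence.** That is sound for participants who stop early. Here the trial itself ends the treatment, so the argument does not carry over.

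**The power figures are crude.** Averaging two visits reduces variance. If 0.3 SD is in per-visit SD units and the two visits correlate at 0.5 (assumption), the variance of their mean is (1 + 0.5)/2 = 0.75 of one visit's. Undiluted power at 160 per arm is then Φ(2.683/√0.75 − 1.96) = 87%, falling to 84%, 77% and 64% for f = 10%, 25% and 50% with r = 0. The level changes; the proportional loss of effect does not.

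**The pharmacological support is thin.** The metformin effect on endothelial function cited in protocol 3.1 was in non-diabetic women with chest pain and normal coronary arteries, and no text addresses loss of effect after stopping. The Visit 1 rule does not show that the protocol foresaw this problem either: a baseline must precede randomisation in any case, and the footnote gives no reason.

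**Conclusion.** The gap is real but modest. An ENDOPAT test inside its window can be off drug at one of the two post-baseline visits, and neither document prevents or handles it. The direction of any error is toward no effect, provided that the effect fades off drug. Its size is unknown. The range of 95% to 75% of the pooled effect rests on assumed late shares of 10% to 50%, complete loss off drug and equal weighting of the visits; half the effect retained halves the loss. One secondary outcome, measured in a subset, is affected.

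Four stronger readings are tempting and are not supported:
- **The primary endpoint is compromised.** Step 5 puts the loss at about 1–4% for a scan 2 to 6 weeks off drug.
- **Power collapses.** For month 36 alone, f = 50% and r = 0 would give 27% power for 0.3 SD at 160 per arm. But the main test is the treatment effect over both visits, the per-visit estimates are exploratory, and nothing supports those values of f and r.
- **Close-out insulin changes also contaminate the test.** This depends on Visit 17 falling one to two weeks after Visit 16, as in Section 10. The schedule heads it month 38, by which time a test within 4 weeks of Visit 16 would normally be done.
- **All three final tests need a one-sided window.** Carotid and retinal structure should change little in a few weeks. A hard cut-off could lose month-36 scans, which the Per Protocol set in SAP 2.1 requires for cIMT.

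**What to change.** **Protocol, ENDOPAT only.** In the schedule and under Visit 16 in Section 10, state that the Visit 16 ENDOPAT is done within the 4 weeks before, or at, Visit 16, and before study medication is collected. Leave the carotid IMT and retinal windows as they are.

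**SAP, for tests already done later.** Record days from last dose to each Visit 16 ENDOPAT. Before unblinding, add a sensitivity analysis that repeats the SAP 2.4.2 model without Visit 16 ENDOPAT tests done after drug collection.

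**Passages to reconcile.**
- The dispensing mark at Visit 16 in the schedule with the Visit 16 text in Section 10.
- The month-38 heading for Visit 17 with the one-to-two-week timing in Section 10.
- The three-week deviation rule in Section 15 with the 4-week test window.

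**Cost.** No new procedure. ENDOPAT booking becomes slightly tighter, and a few month-36 values may be missing that would otherwise have been collected late. Section 17 leaves open whether the change counts as substantial, so that classification is for the sponsor.

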3. INTRODUCTION

Cardiovascular disease (CVD) is the commonest cause of premature death in type 1 diabetes (T1DM).¹⁻⁴ Population-based data from 19,248 individuals with the condition in Scotland indicate ten year absolute CVD event rates of 16.7% and 12.7% respectively in men and women aged 40-60 years ([name], unpublished data presented at JDRF Complications Prevention Workshop, Washington, April 2010), rising to 49% and 39% in those aged over 60 years. These rates are 3-5 fold higher than in the general population. While relative risk is even higher in younger individuals, 95% of actual CVD events occur in those above 40 years of age. The major risk factors are male gender, hypertension, dyslipidaemia, cigarette smoking, hyperglycaemia and nephropathy.

Few randomized controlled trials (RCTs) have directly addressed myocardial infarction (MI) and stroke prevention in T1DM. It is acknowledged in the 2010 American Diabetes Association "Standards of Medical Care"⁵ that recommendations for people with the condition to be prescribed statin therapy to prevent CVD are based on extrapolation from type 2 diabetes,⁶ and on meta-analysis of trials involving a total of 651 people with T1DM in whom CVD event reduction was not statistically significant.⁷ A period of intensive glycaemic control in the Diabetes Control and Complications Trial (DCCT) was associated in later post-randomisation follow up in the Epidemiology of Diabetes and Its Complications (EDIC) study with a reduction in CVD events.^{8,9} Achievement of target glycaemic control is essential for preventing the complications of T1DM, but many years after the DCCT achieving tight glycaemic control remains a challenge for many people living with T1DM. The figures are stark: in the UK, no more than 20% of people with the condition achieve HbA1c < 7.5% and about a third typically have an HbA1c >9% (Scottish Diabetes Survey 2009).¹⁰ With intensified insulin therapy, insulin up-titration aimed at achieving target glycaemia can result in more frequent hypoglycaemia, and - in a significant subpopulation - weight gain, hypertension and dyslipidaemia.^{11,12}

Metformin has many of the properties desirable for an adjunct oral agent to be added in with insulin therapy to improve metabolic control.^{13,14} Data from ourselves and others show that it may: (i) reduce insulin dose (by 6 units) for a given achieved HbA1c; (ii) promote weight stabilization; (iii) be associated with low rates of hypoglycaemia; and (iv) reduce LDL cholesterol - by 0.5 mmol/L (20 mg/dL) - even on a background of statin therapy.¹⁵⁻¹⁸ There is considerable evidence that it may also provide direct and potentially beneficial cardiovascular effects at least in type 2 diabetes - particularly as demonstrated in the UK Prospective Diabetes Study (UKPDS).^{19,20}

Metformin undergoes active transport into cells via the OCT-1 transporter²¹ and activates the AMP-activated protein kinase (AMPK), resulting in decreased hepatic glucose production, increased muscle fatty acid oxidation and improved whole-body insulin sensitivity.²²⁻²⁴ A meta-analysis of its effects in non-diabetic individuals indicates reductions in weight (5%), insulin resistance (23%), LDL cholesterol (6%), and triglycerides (5%).²⁵ In some countries, metformin is relatively frequently co-prescribed with insulin for people with T1DM, particularly those who are overweight. For example, in Tayside, Scotland (2008 data), 9.7% of people with T1DM and BMI>27 kg/m² were currently prescribed metformin, rising to 15.9% for those with BMI>30 kg/m² (*unpublished data*), even although this is not mentioned or advocated in local or national guidelines.

